## **Methods**

Initial efforts for relationship building with a school system have already begun; the PI recently concluded a pilot yoga study in March of 2019 at Park High School, and school and district leadership have expressed a keen interest in continuing this type of intervention for students. For example, in the coming academic year, the school would like to implement this proposed research study, focusing on increasing the number of student participants while gathering additional data for continuous program improvement. [name], district administrator with Park County schools, has also expressed a desire in continuing this research and eventually expanding it to other schools in the district in collaboration with the PI.

In the September 2019, the PI will facilitate a focus group discussion of both male and female high school students at Park High School to gauge student interest in the project and determine best approaches to promote recruitment and retention in the project (particularly with male students). These focus groups will be facilitated through the "Principal Advisory" lunchtime program with the high school principal and PI. Following the focus group discussions, high school participant recruitment will begin with school administrator recommendation for inclusion in the project, and those students will be offered slots in the program first; to allow for maximum recruitment and retention, the intervention will begin in late Fall 2019 between athletic seasons/events. 30-minute sessions will take place twice weekly during the physical education class during the 8-week intervention period. After students have been given an option for inclusion, the program will accept any additional voluntary participation by students within the school, and program recruitment will conclude by the end of 2019. Participation will be voluntary and will be indicated by student signature of the assent form; parent consent will also be required for student participation in this 8-week study. The 30 students to be enrolled in the program will provide written informed consent regarding the scope and details of the study and procedures for participating in the study. The consent form and assent form will include information about participants' rights to end participation at any time during the study.

Incentives for teacher completion of surveys include classroom supply money for teacher completion of surveys (funneled through school administration).

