It is possible that the intervention may bring up strong emotions for the participants; so too might the administration of the ACE survey which will be part of the preliminary data collection (more below). To mitigate this potential, the PI will caution students that this may occur and emphasize the importance of self-care and knowing one's own limits with the intervention. Immediate referrals regarding suicidality, self-harm, depressive thoughts, etc. will be directed to the school nurse. If needed, referrals for additional, outside treatment will be provided as determined by school officials and/or requested by the participant and/or the participant's legal guardian(s). It will also be explained to participants that this study is not designed to be a clinical/psychological intervention but rather an academic intervention, so students that need additional mental health supports will be referred to appropriate outside agencies.

Additional resources for outside assistance will be shared with participants and participant parents/guardians on the assent/consent forms, listing the following avenues for additional help:

- Talking with someone who you can trust
- Calling 911, your doctor or other healthcare provider
- Going to an Emergency Room
- Calling [name] to talk with a crisis worker for free
- Texting 741741 to text with a counselor for free

Visiting NowMattersNow.org to learn skills for dealing with thoughts of suicide

**Aim 1:** Foster a partnership with a rural southwestern Montana school and test the feasibility of implementing a trauma-informed yoga intervention.

For this pilot study, feedback will be gathered from the school district, teachers, and students from the focus group via conversations and/or email communications to determine the level of burden from the various assessment instruments and participation in the pilot; plans and identified needs for this study are ongoing with the school district and the PI. Retention and satisfaction of participants, as measured by survey instrumentation) from year one will indicate the feasibility of an ongoing partnership with the school district, determine possible expansion to the middle school in year two, and will assess both students' and teachers' perception of value of the intervention. Because this is a feasibility study, no control group will be utilized, and the focus of the project will be to examine pre and post survey results and cortisol levels.

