To allow all who are interested to participate in the study, the focus of this project will primarily be to determine feasibility of the intervention; therefore, no control group will be utilized, and the focus of the feasibility trial will be to examine pre and post survey results and cortisol levels. Volunteers will participate in the intervention for 8 weeks. During the intervention phase, the participation goal for each student will be to attend 75% or more of the intervention sessions (attendance will be recorded by the yoga instructor).

After students volunteer for program participation, to establish a baseline for participants, students will be given the ACE screening instrument/ toolkit of pre-surveys and then begin the 8-week intervention. Students will be administered cortisol testing at the beginning of weeks 1 and 4 and the conclusion of week 8 during the intervention, each time prior to the yoga session, and they will complete the post surveys at the conclusion of week 8. At each of the three testing periods, students will provide a saliva sample to the school nurse or PI, to be deidentified (using a code key system) before analysis by the CAIRHE Translational Biomarkers Core Lab at MSU. Testing will use the Abcam (ab154996) cortisol in vitro competitive ELISA (Enzyme-Linked Immunosorbent Assay) kit designed for the accurate quantitative measurement of cortisol in saliva (sensitivity 0.12 ng/ml). Deidentified cortisol data will be returned to the PI for re-identification using the code key. Comparisons using paired t tests between pre and post-surveys will be utilized to determine program efficacy, and any changes in cortisol levels throughout the duration of the program will be analyzed to assess any trends and whether this is a useful measure for the next study phase.

**Aim 3:** Use the preliminary data to modify (as needed) year two of the study for expansion to middle level students and/or increasing the number of high school participants.

This study will utilize descriptive statistics for pre- and post-interventions and analysis of cortisol levels throughout the program to determine the efficacy the intervention.

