## **Statistical Analysis Plan**

Quantitative analyses between pre-intervention (T1) and post-intervention (T2) scores will be utilized for participants who completed the measures at both time points using a paired samples t-test or a Wilcoxon signed rank test with continuity correction for non-normal distributions.

Next, analyses of covariance (ANCOVA) following treatment completion will be used to evaluate whether there are significant post-treatment differences in student-reported symptoms between children with low (0-1), moderate (2-3), and high (4+) ACE scores, with pre-intervention student-reported symptoms and attendance rate as the covariate. The outcome measures to be used in these analyses are the GAD-7, PHQ-A, SDQ, and the SDQ subscales. ANCOVA is the clearest and most straightforward analysis to address each of the analytic goals.

Salivary cortisol samples will be deidentified (using a code key system) before analysis by the CAIRHE Translational Biomarkers Core Lab at Montana State University. Testing utilized the Abcam (ab154996) cortisol in vitro competitive ELISA (Enzyme-Linked Immunosorbent Assay) kit designed for the accurate quantitative measurement of cortisol in saliva (sensitivity 0.12 ng/ml). Comparisons using paired t tests between pre and post-surveys will be utilized to determine program efficacy, and any changes in cortisol levels pre and mid-intervention were analyzed to assess any trends and aided in the decision-making process for whether to continue using this measure for the next study phase.

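### The only cortisol analysis specified for judging whether cortisol is a useful measure is its change in one uncontrolled group, which cannot answer that question

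*Combined protocol and SAP*

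**What the plan says.** **Sampling.** Methods, Aim 2, sets three occasions, all ahead of that day's class: "cortisol testing at the beginning of weeks 1 and 4 and the conclusion of week 8 during the intervention, each time prior to the yoga". No clock time is given. The toolkit surveys are given before the programme and at the end of week 8, not in week 4.

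**Use for the next phase.** In Methods, Aim 2, changes in cortisol through the programme "will be analyzed to assess any trends and whether this is a useful measure for the next study phase". In the Statistical Analysis Plan, "any changes in cortisol levels pre and mid-intervention were analyzed to assess any trends and aided in the decision-making process" on keeping the measure. The SAP does not mention the week 8 sample here.

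**Design.** The Methods plan for 30 students in one group. Aim 1 states: "Because this is a feasibility study, no control group will be utilized". Aim 2 repeats that "no control group will be utilized, and the focus of the feasibility trial will be to examine pre and post survey results and cortisol levels". The calendar is set by the statement that "the intervention will begin in late Fall 2019 between athletic seasons/events".

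**Analysis method.** Aim 2 assigns descriptive statistics to cortisol and paired t tests to the surveys. Under Aim 3, cortisol through the programme also serves to determine efficacy.

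**Other inputs to decisions.** Aim 1 collects feedback on the burden of the assessment instruments. Aim 2 gives decisions on programme improvement and modifications to a community advisory board. Neither passage mentions the cortisol decision.

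**The concern.** Whether a biomarker is worth carrying forward is a question about measurement. Are samples obtained? Are the values quantifiable by the assay? Are they reasonably stable within a student? Do they move with the symptoms they are meant to reflect? The plan collects data that bear on all four, but the only analysis it connects to the decision is change over time.

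That change is a poor guide in either direction. A shift in the group mean over eight weeks from late autumn can come from the programme, from the school term or season, from growing used to sampling, or from differences in sampling time. A flat mean can arise because the programme does not affect cortisol, or because the sample is too small to show an effect. The same cortisol data are also meant to speak to efficacy, so one observed change would have to support both the measure and the programme.

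At stake is one of the few concrete next-phase decisions in the plan. Aim 3 foresees extension to middle-level students, more high-school participants, or both. Keeping an uninformative measure would put saliva sampling and assay cost on them; dropping a workable one would lose it.

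**Working it through.** The documents give no power, effect size, SD or sample-size derivation for cortisol, so there is no stated figure to reproduce.

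**Inputs from the documents:** 30 students, one group, no control; three cortisol occasions in the Methods, two in the SAP's description of the decision; surveys at two time points only.

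**Assumptions:** 24 complete pairs (20% loss from 30); true changes of 0.2 to 0.5 SD of the change; within-student correlation r of 0.2 to 0.6; calendar drift of 0.3 or 0.5 single-occasion SD.

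**1. Precision of a mean paired change.** Half-width in SDs of the change = t(0.975, n−1)/√n.
- n = 30: 2.045/5.477 = 0.373
- n = 24: 2.069/4.899 = 0.422

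**2. How often a real change would be missed.** The plan applies no test to cortisol, so this is an illustration. For a two-sided 5% paired t test, miss rate = 1 − power, from the noncentral t with n−1 degrees of freedom and noncentrality d√n.

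| True change d (SD of change) | Missed, n = 30 | Missed, n = 24 |
|---|---|---|
| 0.2 | 81% | 84% |
| 0.3 | 64% | 71% |
| 0.4 | 44% | 53% |
| 0.5 | 25% | 35% |

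The change detectable with 80% power is 0.53 SD of the change at n = 30 and 0.60 at n = 24.

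**3. How often drift alone would look like a change.** Suppose the programme has no effect and cortisol drifts by b single-occasion SDs. In SDs of the change, d = b/√(2(1−r)).
- b = 0.3: d = 0.24 at r = 0.2 and 0.34 at r = 0.6. The same illustrative test with n = 30 is significant in 24% to 43% of studies.
- b = 0.5: d = 0.40 and 0.56. It is significant in 55% to 84%.

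So both no visible change and a visible change are quite compatible with the opposite conclusion about the measure.

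**4. What measurement statistics could deliver at this size.**
- Within-student repeatability as an intraclass correlation (one-way random effects, F interval). With 30 students and three samples, assumed values of 0.2, 0.4 and 0.6 have 95% intervals of −0.01 to 0.45, 0.18 to 0.62 and 0.40 to 0.77. With two samples they widen to −0.16 to 0.52, 0.06 to 0.66 and 0.32 to 0.79.
- Completeness. If 27 of 30 students gave full sets (assumed), the Wilson 95% interval is 74% to 97%.
- Correlation of cortisol change with symptom change. Near zero the half-width is tanh(1.96/√(n−3)) = tanh(1.96/√27) = tanh(0.377) = 0.36 at n = 30.

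These are imprecise too, but they estimate properties of the measure. The change in the group mean does not.

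**5. The two descriptions of the decision.** The Methods use weeks 1, 4 and 8; the SAP uses pre and mid values. Surveys exist only before the programme and at week 8, so a pre-to-mid cortisol change has no matching symptom change.

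**The case against.** **The plan contains no trend rule.** A reader might infer that cortisol will be kept if it changed and dropped if it did not. The documents do not say so. The Methods name assessing trends and assessing usefulness side by side, and the SAP says only that changes "aided in the decision-making process for whether to continue using this measure for the next study phase". Burden feedback and the advisory board may also play a part. This stands: change is the only cortisol analysis specified for the decision, but it is not shown to be the sole basis.

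**The plan does not test cortisol.** This also stands. Cortisol is analysed descriptively, so the miss rates do not describe a planned procedure, and they depend strongly on the assumed effect. Nor does a 64% miss rate at 0.3 SD mean that a reading of no change is wrong more often than right. It is how often such a reading would occur if the change were real, not how often it would be wrong.

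**This is a feasibility pilot, and responsiveness matters in an outcome measure.** Both are fair. The lack of a control group is a declared choice and not the fault here, and responsiveness may be one consideration. But without a control, an observed change cannot be read as responsiveness to the programme.

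**The alternative statistics are imprecise at n = 30.** True, which argues against a fixed keep-or-drop threshold. Even 24 of 30 complete sets (80%) has a Wilson 95% interval of 63% to 90%.

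**The SAP is partly in the past tense.** New criteria may therefore not be fully prospective there. They can still govern reporting and the justification for year two.

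**Conclusion.** The point holds in a limited form. The only cortisol analysis that the plan links to the usefulness decision is change over the programme. In one uncontrolled group of 30, that change or its absence cannot separate the usefulness of the measure from programme effect, calendar drift and noise. The half-width of 0.37 SD of the change (0.42 at an assumed 24 students) needs no assumed effect size. The illustrative miss rates of 81% to 25% do, and they presuppose a test that the plan does not use. The drift figures rest on assumed drifts and correlations, and a seasonal influence is itself an inference from the late-autumn start. The conclusion follows from the design and does not depend on these illustrations. This is a cheap improvement to a feasibility plan; it does not undermine the study.

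**What to change.** In Methods, Aim 2, and in the Statistical Analysis Plan:

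1. Base the usefulness assessment on data already planned:
   - share of enrolled students with an analysable sample at each wave and at all three;
   - share of values below the 0.12 ng/ml assay sensitivity;
   - within-student correlation across waves, with its confidence interval, read with the caution that true change during the programme also lowers it;
   - correlation of week 1 to week 8 cortisol change with change in GAD-7 and in the depression scale actually administered, with its confidence interval. The documents name that scale variously as SMFQ, Patient Health Questionnaire and PHQ-A, so it needs to be settled.
2. Report mean cortisol change with its 95% confidence interval as descriptive. State that the presence or absence of a group trend alone will not decide whether cortisol is kept.
3. Reconcile the SAP's pre/mid comparison with the three occasions in the Methods.
4. Do not set a numerical keep-or-drop cut-off, such as 80% complete and at most 10% below sensitivity. The documents give no basis for one.

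**Cost:** some wording and a few more descriptive statistics, with no new samples or surveys. Intervals will be wide, about ±0.36 for a correlation near zero at n = 30, and cortisol may be kept for year two without an observed change.

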## **Statistical Analysis Plan**

Quantitative analyses between pre-intervention (T1) and post-intervention (T2) scores will be utilized for participants who completed the measures at both time points using a paired samples t-test or a Wilcoxon signed rank test with continuity correction for non-normal distributions.

Next, analyses of covariance (ANCOVA) following treatment completion will be used to evaluate whether there are significant post-treatment differences in student-reported symptoms between children with low (0-1), moderate (2-3), and high (4+) ACE scores, with pre-intervention student-reported symptoms and attendance rate as the covariate. The outcome measures to be used in these analyses are the GAD-7, PHQ-A, SDQ, and the SDQ subscales. ANCOVA is the clearest and most straightforward analysis to address each of the analytic goals.

Salivary cortisol samples will be deidentified (using a code key system) before analysis by the CAIRHE Translational Biomarkers Core Lab at Montana State University. Testing utilized the Abcam (ab154996) cortisol in vitro competitive ELISA (Enzyme-Linked Immunosorbent Assay) kit designed for the accurate quantitative measurement of cortisol in saliva (sensitivity 0.12 ng/ml). Comparisons using paired t tests between pre and post-surveys will be utilized to determine program efficacy, and any changes in cortisol levels pre and mid-intervention were analyzed to assess any trends and aided in the decision-making process for whether to continue using this measure for the next study phase.

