To protect student privacy, the ACE screening instrument will only quantify how many adverse events the child has experienced, **not** which ones; quantifying ACE scores will help the researcher triangulate the data to determine program efficacy for students with high, moderate, and low ACE scores. School and district administration will have access to anonymous ACE scores for the purpose of collecting demographic information on the participant population. The remainder of the anonymous data collected will be analyzed and reviewed by the community advisory board; decisions regarding program improvement, future implementation, and modifications will be made by the advisory board as well.

For all participants, the primary behavioral health assessments will utilize descriptive statistics and paired t tests with regards to the validated “toolkit” survey of students to address academic, social, and emotional functioning of adolescents (including measures such as the Generalized Anxiety Disorder Scale and Patient Health Questionnaire for Depressive Symptomology) and a Teacher Perception of Student Wellness Survey to assess changes pre-and post-intervention. Descriptive statistics will be utilized with health outcomes to compare pre-and post-intervention cortisol levels. Any secondary academic outcomes will also be analyzed descriptively pre-and post-intervention, as improvement in academic performance may serve as a proxy for improved well-being (attendance records pre-, during, and post-intervention (absences and times arriving late to school), office referral data prior to, during, and post-intervention, and grade average data based on numerical averages in students’ reading and math courses pre- and post-intervention). Baseline data regarding participants’ exposure to childhood trauma as measured by the ACE Self-Reporting Screener will be gathered to determine any relationships between individual ACE scores and outcomes from intervention.

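### The plan states two ACE questions but analyses only the banded one; the question about individual ACE scores has no analysis that uses the count.

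*Combined protocol and SAP*

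**What the plan says.** The Methods (Aim 2) describe the ACE measure as a number per student: "the ACE screening instrument will only quantify how many adverse events the child has experienced". They then give two purposes for it.

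- A banded one: the scores help "to determine program efficacy for students with high, moderate, and low ACE scores".
- An individual one: baseline ACE data are gathered "to determine any relationships between individual ACE scores and outcomes from intervention".

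The Statistical Analysis Plan specifies one ACE analysis, an ANCOVA on post-treatment symptoms "between children with low (0-1), moderate (2-3), and high (4+) ACE scores", "with pre-intervention student-reported symptoms and attendance rate as the covariate". On outcomes it says: "The outcome measures to be used in these analyses are the GAD-7, PHQ-A, SDQ, and the SDQ subscales". Neither the Methods nor the Statistical Analysis Plan includes a regression, correlation or trend test on the count, a reason for the cut-points, or a rule for a sparsely filled band.

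On size and design, the Methods say "The 30 students to be enrolled in the program will provide written informed consent" and "no control group will be utilized, and the focus of the feasibility trial will be to examine pre and post survey results and cortisol levels".

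**The concern.** Cutting the count into three bands treats students with 4 and 8 events as the same and students with 3 and 4 as different. It also spends two degrees of freedom where a linear term spends one. With about 30 students and two covariates already in the model, that matters if symptoms change steadily with each added event.

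What is at stake is the second stated question. A comparison of band means gives no estimate per event, so the study would end without a direct answer to something it says it collects the data for. Aim 3 uses the preliminary data to shape year two, and a slope with its interval would be more useful for that than a band test alone.

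**Working it through.** **Inputs from the documents.** 30 students in one group; ACE recorded as a count; bands 0-1, 2-3 and 4+; covariates baseline score and attendance rate. The plan states no power, effect size, SD, alpha, dropout rate or ACE distribution, so it has no figure to reproduce.

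**Assumptions.** Two-sided inference by F test at alpha 0.05; counts capped at 10; n = 30, or n = 24 for 20% dropout (0.8 × 30 = 24).

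**Step 1: the two models.** Both contain an intercept, baseline score and attendance.

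- Bands: two indicator terms, F on 2 and 30 − 5 = 25 df.
- Count: one linear term, F on 1 and 30 − 4 = 26 df.

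**Step 2: information kept.** The share of variance in the count that lies between bands is 74-85% across five assumed distributions (Poisson with mean 2 and 3, negative binomial of size 2 with mean 2 and about 3, uniform 0-10). Banding therefore discards 15-26%.

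**Step 3: power under a linear relation, by partial correlation r.** Simulation, 4,000 trials per setting, range over the five distributions:

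| r | Count, n = 30 | Bands, n = 30 | Count, n = 24 | Bands, n = 24 |
|---|---|---|---|---|
| 0.3 | 34-35% | 19-22% | 27-29% | 16-18% |
| 0.4 | 57-58% | 32-40% | 46-47% | 26-31% |
| 0.5 | 77-82% | 54-61% | 67-70% | 41-48% |

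With r = 0 both tests reject close to 5% of the time. The gain from the count at n = 30 is 11-16 points at r = 0.3, 17-25 at 0.4 and 19-28 at 0.5.

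**Step 4: the same comparison by slope per event.** Negative binomial counts with mean 2 to 3, n = 30:

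| Slope (residual SD per event) | Count | Bands |
|---|---|---|
| 0.25 | 65-84% | 45-63% |
| 0.12 | 21-31% | 13-18% |

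The two scales connect through r = b·SD / √(1 + b²·SD²). At mean 2 and size 2 the count variance is 2 + 2²/2 = 4, so SD = 2 before the cap. For b = 0.25, r = 0.5/√1.25 = 0.45; for b = 0.12, r = 0.24/√1.0576 = 0.23. Over means 2 to 3 with the cap, b = 0.25 corresponds to r of about 0.44-0.54, which is a large effect.

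**Step 5: other shapes.**

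- Equal steps at the band limits, n = 30: the count runs from about 5 points better to about 5 points worse.
- A jump only at 4+: the bands are better by roughly 4 to 9 points.

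**Step 6: band sizes.** Under negative binomial counts the 4+ band holds 2 to 9 of 30 students (5th to 95th percentile) at mean 2, and about 6 to 14 at mean 3. The chance that some band has fewer than 5 students is 4-60% at n = 30 and 18-84% at n = 24, depending on the distribution.

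**Step 7: leverage.** With skewed counts and n = 30, the most extreme student typically carries about 21-26% of the ACE sum of squares (median over simulated samples).

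**The case against.** The strongest reply is that the bands are planned for a reason. The Methods ask about high, moderate and low scores, and the cut-points are fixed in advance. That stands. A reader might infer that the bands should be reduced to display only, but this would leave the banded question without its test. The gap supports adding an analysis, not replacing one.

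Second, much of the weakness comes from the sample size. At r = 0.3 the count still has only about 35% power with 30 students. It would be wrong to conclude that a graded relation would be missed because of the banding alone.

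Third, the advantage depends on a shape nobody knows. It disappears under a step and reverses slightly under a threshold at 4+. Nor can one assume that the top band will be nearly empty: that follows from a mean of 2, not of 3, and recruitment begins with students recommended by administrators, so the distribution is open.

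Fourth, a reader might fear that a non-significant band comparison will be reported as the programme working equally well at every ACE level. The documents do not say this. With no control group, neither analysis could test it.

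Finally, the aims as headed do not mention ACE and the focus is feasibility, so this is a secondary, exploratory matter. What survives is that one of the two stated ACE questions has no analysis that uses the individual score.

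**Conclusion.** The point holds as a gap in the plan. It is a minor one, worth closing because closing it is nearly free. That the count is banded in the only specified ACE analysis is plain from the text. The size of the loss is conditional on a roughly linear relation and an assumed ACE distribution: about 20 points of power at a large slope, about 8 to 13 at a small one (21 − 13 and 31 − 18), and none or slightly negative under a step or threshold. Adding the count improves the analysis but does not make it adequately powered, so the result should be read as an estimate with its interval. In a single-arm study, either analysis describes how ACE relates to post-programme symptoms given baseline. It does not show whether the programme's effect differs by ACE.

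**What to change.** In the Statistical Analysis Plan:

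1. Add an ANCOVA for each outcome already listed for the ACE analysis, with the ACE count as one linear term and the baseline score and attendance rate as covariates. Name it as the analysis of individual ACE scores, and report the slope per event with a 95% CI.
2. Keep the pre-set band comparison for the high, moderate and low question, and report the number of students in each band.
3. Add a plot of outcome against count, to check linearity and identify influential students.
4. Label both analyses exploratory, and state the limit on interpretation that comes from having no control group.

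**Cost.** A few sentences; no new data, visits or burden. The slope assumes rough linearity, one high-count student can move it, and it adds one exploratory test per outcome. Part of the cortisol text in the Statistical Analysis Plan is in the past tense. If the survey outcomes had also been examined before the change, the added analysis should be labelled post hoc.
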